9.4. Dose Conversion from Prestudy Insulin in Part B

Subjects will record their insulin doses throughout the study. Baseline U-100, U-200, and/or U-300 insulin TDD will be defined as the highest TDD recorded in the 3 days prior to Period 2. All U-100, U-200, and/or U-300 insulin therapy will be discontinued upon initiation of study drug, but permitted prestudy AHA therapy should continue to be taken at prestudy doses, except on clamp assessment days. For all subjects with HbA1c >8.0% at screening, initial U-500R TDD will be the same (in units) as U-100, U-200, and/or U-300 insulin TDD at screening.

For all subjects with baseline HbA1c ≤8.0% at screening, initial U-500R TDD dose will be reduced by 20% from the U-100, U-200, and/or U-300 insulin TDD at screening.

Initial TID dosing will use a 40:30:30 proportion of calculated U-500R TDD for the respective pre-meal doses at 07:00 hours, 12:00 hours, and 18:00 hours, approximately 30 minutes prior to the morning meal, midday meal, and evening meal, respectively.

Initial BID dosing will use a 60:40 proportion of calculated U-500R TDD for the respective pre-meal doses at 07:00 hours and 18:00 hours, approximately 30 minutes prior to the morning meal and evening meal, respectively.

During dose conversion, bolus doses will be rounded down to the nearest 5 U as was done in Study B5K-US-IBHC (Hood et al. 2015). If subjects are using 0.5-mL U-100 insulin syringes, this will be to the closest unit marking (0.01 mL) on the syringe; for those using 1.0-mL U-100 insulin syringes, this will be half way between unit markings (0.02 mL).

Subjects will record SMPG throughout Period 3. During telephone visits (conducted 2 days after the end of Period 2 at a minimum) the investigator or designee will titrate subjects' U-500R dose for each meal according to the algorithms presented in [Table IBHG.9.2](#).

During dose titration (as opposed to initial dosage conversion), conventional rounding to the nearest 5 U will be applied, so that, for instance, values between 120.1 and 122.4 would be rounded down to 120 U while values between 122.5 and 124.9 would be rounded up to 125 U.

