9.4.1. TID Treatment Group Titrations

Subjects in the TID treatment group will have their insulin doses adjusted at a telephone visit 2 to 3 days after the end of Period 2 (at a minimum, additional telephone or office visits may be added for safety as necessary) by the investigator or site designee according to the TID titration algorithm (Table IBHG.9.2).

The U-500R doses will be changed according to corresponding median plasma-equivalent glucose readings from the most recent 3 values at respective times (also see examples below) prior to the telephone or office visit or for any add-on telephone calls or office visits. If even

1 SMPG reading for a given time point is ≤ 70 mg/dL (≤ 3.9 mmol/L), no dosage increase will be applied to the corresponding dose. These adjustments will be applied only to the 2 of the 3 doses (pre-morning meal, pre-midday meal, pre-evening meal) that most need adjustment (that is, the ones with the most out-of-range corresponding median plasma-equivalent glucose readings) at each study visit/interaction.

For subjects receiving U-500R TID, median pre-morning meal and bedtime SMPG values and 03:00 hours SMPG values (if performed) will inform adjustment of the pre-evening meal U-500R insulin dose. When these 3 sets of values provide conflicting guidance, the investigator should base the dose adjustment on the lowest of these results, and prioritize adjustments for hypoglycemic readings ≤ 70 mg/dL (≤ 3.9 mmol/L) over dosage increases.

In all instances, the 10% dosage reduction for values ≤ 70 mg/dL (≤ 3.9 mmol/L) and negation of respective dosage increases for single pre-meal or bedtime hypoglycemic readings should be prioritized over other titration options.

Example 1

A subject assigned to the TID treatment group is taking 300 U TDD with a pre-morning meal dose of 120 U, pre-midday meal dose of 90 U and a pre-evening meal dose of 90 U.

Over the last 3 days, the subject's SMPG values were:

Date	Day 1	Day 2	Day 3
SMPG pre-morning meal, mg/dL (mmol/L)	102 (5.7)	110 (6.1)	135 (7.5)
SMPG pre-midday meal, mg/dL (mmol/L)	163 (9.1)	180 (10.0)	200 (11.1)
SMPG pre-evening meal, mg/dL (mmol/L)	240 (13.3)	221 (12.3)	238 (13.2)
SMPG at bedtime, mg/dL (mmol/L)	130 (7.2)	160 (8.9)	125 (6.9)
SMPG at 03:00 hours, mg/dL (mmol/L)			92 (5.1)

Abbreviation: SMPG = self-monitored plasma glucose.

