SMPG at bedtime, mg/dL (mmol/L)	102 (5.7)	135 (7.5)		165 (9.2)
SMPG at 03:00 hours, mg/dL (mmol/L)		100 (5.6)		

Abbreviation: SMPG = self-monitored plasma glucose.

The investigator should consider changing only the 2 doses that most need adjustment. In this instance, the 2 doses that appear to most need adjustment are pre-evening meal and pre-morning meal because the median glucose values at pre-morning meal and pre-evening meal are the most outside of the target range. The median pre-morning meal SMPG (148 mg/dL [8.2 mmol/L]) is within the range of 131 to 180 mg/dL (7.3 to 10.0 mmol/L) calling for a 5% dose increase of pre-evening meal dosage. However, the unexplained hypoglycemia (66 mg/dL [3.7 mmol/L]) takes precedence and accordingly, there should be no upward evening meal dosage adjustment. The median of the last 3 readings for pre-evening meal SMPG (68 mg/dL [3.8 mmol/L]) is \leq 70 mg/dL (\leq 3.9 mmol/L); therefore, the investigator would reduce the pre-midday meal dose by 10% to 81 U, which is rounded to 80 U, the nearest 5 U.

9.4.2. *BID Treatment Group Titrations*

Subjects in the BID treatment group will have their insulin dosages adjusted at each study visit (office and telephone or for add-on visits) by the investigator or site designee according to the BID titration algorithm ([Table IBHG.9.2](#)).

Human regular U-500 insulin doses will be changed according to corresponding median plasma-equivalent glucose readings from the most recent 3 values at respective times (also see examples below) prior to the scheduled telephone or office visit or for any add-on visits. If even 1 of the SMPG readings for a given time point is ≤ 70 mg/dL (≤ 3.9 mmol/L), no dosage increase will be applied to the corresponding dose. These adjustments will be applied to both doses as indicated (pre-morning meal and pre-evening meal) at each study visit/interaction.

For subjects receiving U-500R BID, median pre-morning and bedtime SMPG values and 03:00 hours SMPG values (if performed) will inform adjustment of the pre-evening meal U-500R insulin dose, and both median pre-evening meal and pre-midday meal SMPG values will inform adjustment of the pre-morning meal U-500R insulin dose. When these sets of values provide conflicting guidance, investigators should base the dose adjustment on the lowest of these results, and prioritize adjustments for hypoglycemic readings ≤ 70 mg/dL (≤ 3.9 mmol/L) over dosage increases.

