In all instances, the 10% dosage reduction for median pre-meal/bedtime values or single 03:00 hours glucose values ≤ 70 mg/dL (≤ 3.9 mmol/L) and negation of respective dosage increases for single pre-meal or bedtime hypoglycemic readings should be prioritized over other titration options.

Example 1:

A subject assigned to the BID treatment group is taking 300 U TDD, with a pre-morning meal dose of 180 U and a pre-evening meal dose of 120 U.

Over the last 4 days, the subject's SMPG values were:

Date	Day 1	Day 2	Day 3	Day 4
SMPG pre-morning meal, mg/dL (mmol/L)	180 (10.0)	160 (8.9)	200 (11.1)	
SMPG pre-midday meal, mg/dL (mmol/L)		120 (6.7)	170 (9.4)	132 (7.3)
SMPG pre-evening meal, mg/dL (mmol/L)	200 (11.1)		225 (12.5)	260 (14.4)
SMPG at bedtime, mg/dL (mmol/L)	142 (7.9)		128 (7.1)	110 (6.1)
SMPG at 03:00 hours, mg/dL (mmol/L)	101 (5.6)			

Abbreviation: SMPG = self-monitored plasma glucose

The median pre-evening meal SMPG value is 225 mg/dL (12.5 mmol/L); therefore, the subject's pre-morning meal dose should be increased by 15% to 207 U, rounded down to 205 U. The median pre-morning meal SMPG value is 180 mg/dL (10.0 mmol/L); therefore, the subject's pre-evening meal dose should be increased by 5% to 126 U, rounded down to 125 U.

Example 2:

A subject assigned to the BID treatment group is taking 250 U TDD, with a pre-morning meal dose of 150 U and a pre-evening meal dose of 100 U.

Over the last 4 days, the subject's SMPG values were:

Date	Day 1	Day 2	Day 3	Day 4
SMPG pre-morning meal, mg/dL (mmol/L)		138 (7.7)	130 (7.2)	110 (6.1)
SMPG pre-midday meal, mg/dL (mmol/L)	80 (4.4)	71 (3.9)	58 (3.2)	
SMPG pre-evening meal, mg/dL (mmol/L)	160 (8.9)		200 (11.1)	182 (10.1)
SMPG at bedtime, mg/dL (mmol/L)	140 (7.8)		132 (7.3)	110 (6.1)
SMPG at 03:00 hours, mg/dL (mmol/L)		142 (7.9)		

Abbreviation: SMPG = self-monitored plasma glucose.

The median pre-evening meal SMPG is 182 mg/dL (10.1 mmol/L); thus, the subject's pre-morning meal dose would normally be increased by 10%. However, there is a single pre-midday meal hypoglycemic reading (58 mg/dL [3.2 mmol/L]); therefore, the pre-morning meal dose should not be increased. The median pre-morning meal SMPG value is 130 mg/dL (7.2 mmol/L); therefore, the subject's pre-evening meal dose should not change.

Example 3:

A subject assigned to the BID treatment group is taking 275 U TDD with a pre-morning meal dose of 165 U and a pre-evening meal dose of 110 U.

Over the last 3 days, the subject's SMPG values were:

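### Part B dosing text is inconsistent in two places: BID Example 1 doses above the natural reading of the lowest-result rule, and Section 9.4 converts from screening TDD rather than the pre-Period 2 TDD it defines

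*Protocol*

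**What the plan says.** **Titration (Protocol 9.4.2).** The pre-evening and pre-midday medians together inform the BID morning dose. The fasting (pre-morning) median, the bedtime median and any 03:00 value inform the evening dose. The tie-break is: "When these sets of values provide conflicting guidance, investigators should base the dose adjustment on the lowest of these results". Section 9.4.1 has the same sentence for the TID evening dose: "When these 3 sets of values provide conflicting guidance, the investigator should base the dose adjustment on the lowest of these results". Neither section defines conflicting guidance.

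**BID Example 1 (9.4.2).** The subject takes 180 U in the morning and 120 U in the evening. The example concludes that the "pre-morning meal dose should be increased by 15% to 207 U, rounded down to 205 U", citing only the pre-evening median, and that the "pre-evening meal dose should be increased by 5% to 126 U, rounded down to 125 U", citing only the fasting median.

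**Starting dose (Protocol 9.4).** Baseline "insulin TDD will be defined as the highest TDD recorded in the 3 days prior to Period 2". The next two sentences, one for each HbA1c stratum, set the initial U-500R dose from the prestudy total daily dose (TDD) at screening. Section 7.1.3 bases it on the TDD before admission for Period 2. Section 9.3 uses the highest TDD in the 3 days before Period 2.

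**The concern.** Site staff start and adjust self-injected 500 U/mL insulin from these sentences, and they learn a titration algorithm largely from its worked examples. BID Example 1 appears in the same section as a cautious rule and arrives at higher doses than the natural reading of that rule gives. Two staff members could reach different doses from one diary, one following the sentence and the other the example. The conversion text has the same weakness: one section names two different dates for the dose it starts from. What is at stake is dosing safety and consistency in Part B, not the inference.

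**Working it through.** **Inputs.** Readings and starting doses come from BID Example 1. The dose bands come from Table IBHG.9.2: 70 or below, −10%; 71–130, no change; 131–180, +5%; 181–220, +10%; above 220, +15%. Titrated doses round to the nearest 5 U (Section 9.4). The table's row labels are damaged in the copy read, so only the bands are used; they are the same in every legible row.

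**Values in BID Example 1 (mg/dL).**

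| Time point | Readings | Value used | Band |
|---|---|---|---|
| Fasting | 180, 160, 200 | median 180 | +5% |
| Pre-midday | 120, 170, 132 | median 132 | +5% |
| Pre-evening | 200, 225, 260 | median 225 | +15% |
| Bedtime | 142, 128, 110 | median 128 | none |
| 03:00 | 101 | 101 | none |

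**Reproducing the printed doses.** Morning, from the pre-evening median alone: 180 × 1.15 = 207, rounded to 205 U. Evening, from the fasting median alone: 120 × 1.05 = 126, rounded to 125 U. Total 205 + 125 = 330 U/day, against 300 at the start (+10.0%). The arithmetic is right, but each dose rests on the highest of its informing values.

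**Applying the lowest-result rule.** Morning: min(132, 225) = 132, so 180 × 1.05 = 189, rounded to 190 U. Evening: min(180, 128, 101) = 101, so the dose stays at 120 U. Total 190 + 120 = 310 U/day (+3.3%).

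**The excess depends on what counts as conflicting.**

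| Meaning of conflicting | Doses (U) | U/day | Printed minus rule |
|---|---|---|---|
| Any difference in indicated step | 190 + 120 | 310 | 20 (6.5% of 310) |
| Change versus no change, but not +5% versus +15% | 205 + 120 | 325 | 5 (1.5% of 325) |
| Increase versus decrease only | rule not triggered | – | 0 |

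In the last row the text still does not say which of several agreeing values sets the step, so 205 U and 125 U cannot be derived from the rule alone.

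**The other examples, for the doses the rule covers.**
- BID Example 2: morning min(71, 182) = 71, no change, 150 U; evening min(130, 132, 142) = 130, no change, 100 U. Both match.
- BID Example 3: morning min(128, 70) = 70, 165 × 0.90 = 148.5, rounded to 150 U; evening min(141, 108, 70) = 70, 110 × 0.90 = 99, rounded to 100 U. Both match.
- TID evening doses: Example 1 (110, 130, 92), no change; Example 2 (03:00 value 60), −10%, 54 rounded to 55 U; Example 3 (148, 135, 100), no change. All match.

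So five of the six examples end at the rule's dose. The reasoning in two of them nevertheless starts from a single governing reading. BID Example 2 says the "pre-morning meal dose would normally be increased by 10" per cent, although its pre-midday median of 71 calls for no change. TID Example 3 treats the fasting median as "calling for a 5% dose increase of pre-evening meal dosage", although the 03:00 value of 100 does not. In both, a low reading then blocks the increase.

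**Starting dose.** Screening may fall up to 28 days before Period 1, and Periods 1 and 2 may be up to 21 days apart, so the two TDD dates can differ by up to 28 + 21 = 49 days. If the two TDDs differ by d units, the initial U-500R dose differs by d (HbA1c above 8.0%) or 0.8d (HbA1c 8.0% or below), before each dose is rounded down to 5 U. The documents give no value for d.

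**The case against.** The strongest defence is that conflicting guidance may mean guidance in opposite directions. No reading in BID Example 1 calls for a decrease, so the rule would not apply and the printed doses would stand. A governing reading (pre-evening for the morning dose, fasting for the evening dose) with a hypoglycemia override also reproduces all three BID examples. This part of the defence holds: a reader might infer that the example breaks the rule however it is read, or that the excess is at least 5 U/day, and neither follows while the term is undefined. It does not remove the problem, because Section 9.4.2 states neither that narrow meaning nor a governing reading.

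A reader might also infer that the examples in both sections are generally at odds with the rule, or that TID Example 3 should have raised the morning dose. The documents do not support this. The other five examples end at the rule's doses. In TID Example 3, adjustments go "These adjustments will be applied only to the 2 of the 3 doses" whose medians are furthest out of range. The low pre-evening median takes priority, and the fasting median of 148 then ranks ahead of the pre-midday 142. An isolated slip in BID Example 1 is a fair explanation, and an undamaged Table IBHG.9.2 might help show what was intended.

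On the starting dose, the defence is that Sections 7.2, 9.2 and 9.3 expect a stable prestudy dose, so the two TDDs should be close. That limits the effect but leaves the wording contradictory.

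**Conclusion.** Both inconsistencies are in the current protocol text, and both are minor. BID Example 1 prints 20 U/day more than the plain reading of the lowest-result rule (330 versus 310 U/day); the possible range is 0 to 20 U/day, depending on an undefined term. The conversion sentences contradict Sections 7.1.3 and 9.3 and 9.4's own definition; the size cannot be computed and should be small if the prestudy TDD is held stable as planned.

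A reader might infer a serious safety failure or a threat to the results. The documents do not support either. Titration is for safety where needed, and a single informing reading of 70 mg/dL or below blocks an increase. A 03:00 check follows any increase, and the investigator may deviate from the algorithm for the subject's safety. Part B has no formal statistical analysis, and the Part A comparison and the sample size are unaffected.

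**What to change.** 1. In 9.4.1 and 9.4.2, define conflicting guidance to include differing step sizes, and correct BID Example 1 to 190 U and 120 U. If the sponsor's clinicians instead intend a single governing reading with a hypoglycemia override, rewrite the lowest-result sentence in both sections to say so and name the governing reading for each dose.
2. Check that Table IBHG.9.2 and the wording of BID Example 2 and TID Example 3 agree with the rule chosen.
3. In both conversion sentences of 9.4, replace TDD at screening with the pre-Period 2 baseline TDD already defined there. HbA1c stays at screening.
4. Send the site a short re-training note.

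The cost is wording corrections and the note. Design, sample size and analysis stay as they are.

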9.5. Specific Restrictions/Requirements

Prior to beginning the study, the subjects will complete informed consent and baseline tests.

Throughout the study, subjects may undergo medical assessments and review of compliance with restrictions before continuing in the study.

Meals/Diet – For all treatment periods, subjects will be fasted from approximately 12 hours prior to clamp initiation until after the clamp procedure is completed. Water can be consumed freely during this period.

When at home, subjects will be encouraged to maintain their body weight and consume their normal diets.

Alcohol – No alcohol will be allowed from at least 24 hours prior to clamp initiation and while resident in the CRU.

Smoking – Subjects will refrain from smoking, using electronic cigarettes, or using nicotine replacement therapy while resident in the CRU.

Exercise – Subjects will be encouraged to maintain their regular exercise; however, they should not undertake vigorous or prolonged exercise within 48 hours prior to each clamp day.

After dosing, and during the clamp procedure, subjects should remain recumbent or sitting in the CRU. Movement will be restricted to retain integrity of connections to infusion and study procedures.

Authorization to leave the CRU must be given by a physician.

9.6. Blinding

This is an open-label study.

9.7. Concomitant Therapy

Subjects on stable concomitant medication at the time of study entry should continue their regular, unchanged dose throughout the study; for example, hormonal contraceptives, thyroid replacement therapy, anti-hypertensives, low-dose aspirin, and cholesterol lowering agents. Prescription medications (other than those allowed in Inclusion Criteria [4] and [5]), herbal medications, or nutritional supplements that affect PG or insulin sensitivity, or promote weight loss will not be allowed within 4 weeks prior to dosing. Initiation of new over-the-counter medication within 7 days prior to dosing, or prescription medication or herbal medication within 14 days prior to dosing may be permitted following discussion with the Lilly clinical pharmacologist. Vitamin/mineral supplements and/or occasional use of acetaminophen will be allowed.

Subjects may continue to take their stable prestudy AHA dose (MET, dipeptidyl peptidase-4 inhibitors, pioglitazone [doses ≤ 30 mg/day], GLP-1 receptor agonists, and/or SGLT2 inhibitors [not in combination with GLP-1 receptor agonists]), unchanged, throughout the study, except on clamp assessment days.

Rosiglitazone, pramlintide, once weekly or BID exenatide, other injectable or oral AHAs not listed in Inclusion Criterion [5], or permitted AHAs taken at doses other than that prescribed by the product label will not be allowed.

If the need for concomitant medication arises, inclusion or continuation of the subject may be at the discretion of the investigator after consultation with a Lilly clinical pharmacologist or CRP/clinical research scientist. Any additional medication used during the course of the study must be documented.

10. Sample Collection and Safety Data Collection

[Attachment 1](#) lists the schedule for sample collections in this study.

[Attachment 2](#) lists the clinical laboratory tests that will be performed for this study.

[Attachment 3](#) summarizes the blood volumes for all blood sampling during the study.

10.1. Laboratory Samples

Blood samples will be collected to determine whether subjects meet inclusion/exclusion criteria and to monitor subject health.

Investigators must document their review of each laboratory safety report.

Samples collected for specified laboratory tests will be destroyed within 60 days of receipt of confirmed test results. Tests are run and confirmed promptly whenever scientifically appropriate. When scientific circumstances warrant, however, it is acceptable to retain samples to batch the tests run, or to retain the samples until the end of the study to confirm that the results are valid. Certain samples may be retained for a longer period, if necessary, to comply with applicable laws, regulations, or laboratory certification standards.

10.2. Samples for Pharmacokinetic and Pharmacodynamic Evaluations

10.2.1. Pharmacokinetic Samples

At the visits and times specified in the Study Schedule, venous blood samples of approximately 3.5 mL and 2.5 mL each will be collected to determine the serum IRI and C-peptide concentrations, respectively. Instructions for the collection and handling of blood samples will be provided by the sponsor. The actual date and time (24-hour clock time) of each sampling will be recorded.

10.2.2. Bioanalysis

Samples will be analyzed at a laboratory approved by the sponsor and stored at a facility designated by the sponsor.

Concentrations of IRI will be assayed using a validated enzyme linked immunosorbent assay (ELISA) method for the quantitative determination of IRI. This method measures endogenous insulin, as well as exogenous biosynthetic insulin, after a pretreatment of the sample with polyethylene glycol to remove anti-insulin antibodies. C-peptide measurements will be used to correct for endogenous insulin production.

Bioanalytical samples collected to measure investigational product concentrations will be retained for a maximum of 1 year following last subject visit for the study.

10.2.3. Pharmacodynamic Evaluations (Glucose Clamp Procedure)

The aim of the euglycemic glucose clamp is to maintain euglycemia through glucose infusion after the administration of a dose of insulin. During the glucose clamp, the GIR will be adjusted to maintain a predetermined target blood glucose (BG) concentration for the individual subject. The BG concentration will be maintained within approximately $\pm 5\%$ of the predose target value, which will be defined as 120 mg/dL (6.7 mmol/L).

Thus BG concentrations will be kept constant while GIR varies. The varying GIR will reflect the PD activity of insulin.

Subjects will participate in euglycemic clamps on 3 separate visits. Clamp procedures in Part A will last up to 24 hours after dosing, and clamp procedures in Part B will last 24 hours. The GIRs required to maintain euglycemia and BG concentrations will be documented throughout the procedure. If a clamp cannot be completed due to logistical reasons (for example, lack of venous access), the subject may return on 1 additional occasion for the clamp assessment.

